## PROTOCOL HISTORY

Protocol		Associated Country-Specific Protocols		
Version	Date Final	Country	Version	Date Final
4	See electronic date stamp on title page	—	—	—
3	18 September 2020	—	—	—
2	23 April 2020	Belgium	2	30 July 2020
		Norway	2	10 May 2020
1	25 November 2019	—	—	—

## **PROTOCOL AMENDMENT, VERSION 4 RATIONALE**

Protocol GO41582 has been amended to add the option to implement up to three dose-escalation arms in a given dose cohort to mitigate the risk of infusion-related reactions (IRRs). These dose-escalation arms differ in the schedule of RO7297089 administration in Cycle 1. In addition, this amendment modifies eligibility criteria related to serum monoclonal protein (M-protein) levels and serum calcium levels. Changes to the protocol, along with a rationale for each change, are summarized below.

The following changes have been incorporated in Version 4:

- Section 3.1.1 has been revised to add an option for up to three dose-escalation arms in a dose cohort. These dose-escalation arms define the Cycle 1 administration schedule for RO7297089 and include a flat-dose arm (Arm A), a split-dose arm (Arm B), and a step-dose arm (Arm C). The criteria for the opening and enrollment into each of these arms are also described.
- Additional changes regarding the dose-escalation arms are as follows:
  - Section 3.1.3 has been revised to specify that RO7297089 administration for the first cycle after inpatient dose escalation may follow any administration schedule previously evaluated in the study.
  - Section 3.1.5 has been revised to specify that the Internal Safety Committee (ISC) will make decisions in consultation with study investigators regarding opening Arm B and/or Arm C for a given dose cohort.
  - Section 3.3.2 has been revised to include rationale for the dose-escalation arms.
  - Section 4.3.2.1 has been revised to include additional dosing instructions regarding the additional dose-escalation arms.
  - Section 4.5.5 has been revised to include additional vital sign monitoring instructions regarding the additional dose-escalation arms.
  - Appendix 1 and Appendix 3 have been revised to reflect the additional timepoints and assessments regarding the additional dose-escalation arms.
- Section 4.1.1 has been revised to update the inclusion criterion for serum M-protein concentration from  $\geq 1.0$  g/dL ( $\geq 10$  g/L) to  $\geq 0.5$  g/dL ( $\geq 5$  g/L). This revision was made on the recommendation of investigators based on the patient population for this study. Additionally, at least three historical values for serum M-protein (or serum free light chains [SFLC], if light chain-only disease) from the end of prior therapy to the initiation of study treatment with RO7297089 will be collected if available (Section 4.5.6 and Appendix 1).

- Section 4.1.1 has been revised to update the inclusion criterion for serum calcium concentration (corrected for albumin) from a threshold of the upper limit of normal (ULN) to a threshold of  $\leq 11.5$  mg/dL (2.9 mmol/L). This new threshold is consistent with NCI CTCAE v5.0 guidelines for hypercalcemia and removes the threshold variability that occurs when local laboratory ranges are used.
- Section 4.1.2 has been revised to clarify the exclusion criterion regarding previous treatment with systemic immunosuppressive medications.
- Section 5.1.1.1 has been revised to provide recent information regarding IRR events in this study and to reiterate premedication instructions accordingly.

Additional minor changes have been made to improve clarity and consistency. Substantive new information appears in italics. This amendment represents cumulative changes to the original protocol.

## PROTOCOL SYNOPSIS

**TITLE:** AN OPEN-LABEL, MULTICENTER, PHASE I TRIAL EVALUATING THE SAFETY AND PHARMACOKINETICS OF ESCALATING DOSES OF RO7297089 IN PATIENTS WITH RELAPSED OR REFRACTORY MULTIPLE MYELOMA

**PROTOCOL NUMBER:** GO41582

**VERSION NUMBER:** 4

**EUDRACT NUMBER:** 2019-003540-76

**IND NUMBER:** To be determined

**NCT NUMBER:** NCT04434469

**TEST PRODUCT:** RO7297089 (BPCT2605S)

**PHASE:** I

**INDICATION:** Relapsed or refractory multiple myeloma

**SPONSOR:** Genentech, Inc.

### OBJECTIVES AND ENDPOINTS

This study will evaluate the safety and pharmacokinetics of RO7297089 in patients with relapsed or refractory (R/R) multiple myeloma (MM) and make a preliminary assessment of anti-tumor activity. Specific objectives and corresponding endpoints for the study are outlined below.

#### **Safety Objective (Primary Study Objective)**

The safety objective for this study is to evaluate the safety of RO7297089, including estimation of the maximum tolerated dose (MTD) and characterization of dose-limiting toxicities (DLTs), on the basis of the following endpoints:

- Incidence and severity of adverse events, including DLTs, with severity determined according to National Cancer Institute Common Terminology Criteria for Adverse Events, Version 5.0 (NCI CTCAE v5.0) and the Modified Cytokine-Release Syndrome Grading System
- Change from baseline in targeted vital signs
- Change from baseline in targeted ECG parameters
- Change from baseline in targeted clinical laboratory test results
- Relationship between RO7297089 dose and safety, pharmacokinetic (PK), activity, and immunogenicity endpoints

#### **Pharmacokinetic Objectives**

The PK objective for this study is to characterize the RO7297089 PK profile on the basis of the following endpoints:

- Serum concentration of RO7297089 at specified timepoints
- PK parameters for RO7297089

The exploratory PK objectives for this study are as follows:

- To evaluate potential relationships between drug exposure and the safety and activity of RO7297089 on the basis of the following endpoints:

- Relationship between serum concentration or PK parameters for RO7297089 and safety endpoints
- Relationship between serum concentration or PK parameters for RO7297089 and activity endpoints
- To evaluate potential relationships between selected covariates and exposure to RO7297089 on the basis of the following endpoint:
  - Relationship between selected covariates and serum concentration or PK parameters for RO7297089

#### **Activity Objectives**

The activity objective for this study is to make a preliminary assessment of the activity of RO7297089 on the basis of the following endpoints:

- Objective response rate, defined as a stringent complete response, complete response, very good partial response, or partial response, as determined by the investigator according to International Myeloma Working Group (IMWG) Uniform Response Criteria
- Duration of response, defined as the time from the first occurrence of a documented objective response to disease progression or death from any cause (whichever occurs first), as determined by the investigator according to IMWG Uniform Response Criteria

#### **Immunogenicity Objectives**

The immunogenicity objective for this study is to evaluate the immune response to RO7297089 on the basis of the following endpoint:

- Prevalence of anti-drug antibodies (ADAs) at baseline and incidence of ADAs during the study

The exploratory immunogenicity objective for this study is to evaluate potential effects of ADAs on the basis of the following endpoint:

- Relationship between ADA status and safety, PK, biomarker, or activity endpoints

#### **Biomarker Objective**

The exploratory biomarker objective for this study is to identify and/or evaluate biomarkers that are predictive of response to RO7297089 (i.e., predictive biomarkers), are early surrogates of activity, are associated with progression to a more severe disease state (i.e., prognostic biomarkers), are associated with acquired resistance to RO7297089, are associated with susceptibility to developing adverse events or can lead to improved adverse event monitoring or investigation (i.e., safety biomarkers), can provide evidence of RO7297089 activity (i.e., pharmacodynamic [PD] biomarkers), or can increase the knowledge and understanding of disease biology and drug safety, on the basis of the following endpoint:

- Relationship between biomarkers in blood and tissue samples (listed in the protocol) and safety, PK, activity, immunogenicity, or other biomarker endpoints

#### **Additional Objective**

An additional objective for this study is to identify a recommended Phase II dose (RP2D) and regimen for RO7297089 on the basis of the following endpoint:

- Relationship between RO7297089 exposure and safety, PK, activity, and immunogenicity endpoints

### **STUDY DESIGN**

#### **Description of Study**

This is a first-in-human Phase I, open-label, multicenter, global, dose-escalation study designed to evaluate the safety, tolerability, and pharmacokinetics of RO7297089 and make a preliminary assessment of anti-tumor activity in patients with R/R MM for whom no established therapy for MM is appropriate and available or who are intolerant to those established therapies. The study consists of a screening period of up to 28 days and a minimum follow-up period of 90 days after treatment. Following confirmation of eligibility, patients will receive RO7297089 by IV infusion. Patients will be enrolled in two stages: a dose-escalation stage and an expansion stage. *To mitigate the risk of infusion-related reactions (IRRs), up to three dose-escalation arms that*

differ in the RO7297089 administration schedule for Cycle 1 may be enrolled in a dose-escalation cohort. The study will enroll approximately 30–50 patients during the dose-escalation stage and approximately 30 patients during the expansion stage at approximately 12 sites globally.

Patients who do not meet the criteria for participation in this study (screen failure) may qualify for one re-screening opportunity (for a total of two screenings per participant) at the investigator's discretion. Patients must re-sign the consent form prior to re screening. The investigator will record reasons for screen failure in the screening log.

All patients will be closely monitored for adverse events throughout the study and for at least 90 days after the final dose of study treatment. Adverse events will be graded according to the NCI CTCAE v5.0, with the exception of cytokine-release syndrome (CRS), which will be graded according to the Modified Cytokine-Release Syndrome Grading System.

Patients may continue treatment with RO7297089 until disease progression as determined by the investigator using IMWG Uniform Response Criteria, unacceptable toxicity, start of new anti-cancer therapy, or withdrawal from study participation, whichever occurs first.

### **Dose-Escalation Stage**

Approximately 30–50 patients will be enrolled in the dose-escalation stage. The dose-escalation stage of the study will assess the safety, tolerability, and pharmacokinetics of RO7297089 administered by IV infusion. *The cycle length is 14 days.*

*To mitigate the risk of IRRs, up to three dose-escalation arms may be enrolled in a given dose cohort. These arms differ in the RO7297089 administration schedule for Cycle 1:*

- **Arm A (Flat Dose-Escalation Arm).** *Patients in Arm A will receive the Cycle 1 target dose of RO7297089 as a flat dose independent of body weight on Day 1 and Day 8. Dosing for Cycle 2 and beyond will follow the same administration schedule. The DLT assessment window for Arm A is 14 days (Cycle 1, Days 1–14).*
- **Arm B (Split Dose-Escalation Arm).** *Patients in Arm B will receive the first dose in Cycle 1 as a split dose. The initial target dose of RO7297089 will be divided over 2 days (Days 1 and 2), and the full target dose will be administered on Day 8.*

*Initially, the dose will be divided such that 50% of the target dose is administered on Day 1 and the remaining 50% on Day 2. If the Day 1 dose is associated with a Grade  $\geq 2$  IRR, the ratio may be adjusted for subsequent patients so that a smaller percentage of the dose is administered on Day 1, with the remainder of the dose administered on Day 2. For example, 25% of the target dose administered on Day 1 and the remaining 75% administered on Day 2.*

*If a patient does not receive the full planned dose on Day 1 because of scheduling reasons but has received at least 75% of the intended Day 1 dose, the patient may proceed with the Day 2 infusion to receive the remainder of the full target dose.*

*For Cycle 2 and beyond, RO7297089 will be administered on Day 1 and Day 8 of each 14-day cycle. The DLT assessment window for Arm B is 14 days (Cycle 1, Days 1–14).*

- **Arm C (Single-Step Dose-Escalation Arm).** *Patients in Arm C will receive the first cycle of RO7297089 as a single-step dose escalation. The Cycle 1, Day 1 dose will be 60 mg, followed by the full target dose on Day 8. For Cycle 2 and beyond, the target dose of RO7297089 will be administered on Day 1 and Day 8 of each 14-day cycle. The DLT assessment window for Arm C is 14 days (Cycle 1, Day 8 to Cycle 2, Day 7, to allow for two target doses); the window excludes the Cycle 1, Day 1 60-mg dose, which has already cleared.*

*For all arms, the target dose refers to the highest dose administered in Cycle 1; this target dose will be administered on Day 1 and Day 8 of subsequent cycles.*

*Enrollment in the dose-escalation arms will be managed as follows:*

- *For new dose cohorts, all patients will enroll in Arm A unless criteria have been met for opening Arms B or C in a previous cohort.*

- *Arm B may open if the planned infusion time for Arm A exceeds 4 hours on Cycle 1, Day 1. Arm C may open if 2 or more patients in Arm B of that dose cohort experience any grade IRR that precludes the patient from receiving the full target dose during Cycle 1, Day 1 and Day 2.*
- *Once Arm B is open, Arm A for that dose cohort may close to further enrollment and may not open for subsequent dose cohorts. Similarly, once Arm C is open, Arm B for that dose cohort may close to further enrollment and may not open for subsequent dose cohorts.*
- *A minimum of 3 patients must complete the DLT assessment period for a given arm (Arm A, B, or C) before dose escalation for that arm may occur.*

Dose escalations will be guided by the modified continual reassessment method of escalation with overdose control (mCRM-EWOC) model (Neuenschwander et al. 2008). All cohorts will enroll a minimum of 3 patients. Enrollment of the first 2 patients in each *arm of each* dose-escalation cohort will be staggered such that the respective Cycle 1, Day 1 treatments are administered  $\geq 72$  hours apart. The maximal dose escalation increment recommended by the model will be 3-fold. In addition, the relevant demographic, adverse event, laboratory, dose administration, and available PK data will be reviewed prior to dose-escalation decisions, which will be made by an Internal Safety Committee (ISC) in consultation with the investigator.

Evidence of clinical activity at a given dose level (e.g., decrease in serum monoclonal protein [M-protein]) or PD activity (e.g., NK cell activation) may ungate backfill cohorts at doses that have already completed DLT assessment and have been found not to exceed the MTD in escalation cohorts. DLT information from patients in these back-fill cohorts will be used to inform the mCRM-EWOC model.

Patients will be closely monitored for adverse events during a DLT assessment window (14 days), *as defined above for each arm*. Adverse events identified as DLTs, as defined below, will be reported to the Sponsor within 24 hours.

Patients who discontinue from the study prior to completing the DLT assessment window for reasons other than a DLT will be considered non-evaluable for dose-escalation decisions and MTD assessments and will be replaced by an additional patient at that same dose level. Patients must receive two *planned target* doses of RO7297089 during the DLT assessment window to be considered DLT-evaluable. Treatment delays during the first cycle of RO7297089 will be allowed if they are less than one cycle (i.e., <14 days); under these circumstances, the DLT assessment window may be extended up to *an additional 7* days in order to capture two *planned target* doses of treatment. Patients who receive supportive care during the DLT assessment window that confounds the evaluation of DLTs (not including supportive care described below as part of the DLT definition) may be replaced at the discretion of the Medical Monitor.

As described below, the ISC will additionally review cumulative safety data and make recommendations regarding overall study conduct to ensure patient safety while receiving study treatment. These recommendations include suspending patient enrollment based on the overall benefit-risk profile of RO7297089 during dose escalation.

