**Arm A (Flat Dose)**

**Arm B (Split Dose)a**

**Arm C (Step Dose)c**

D = day; DLT = dose-limiting toxicity; IRR = infusion-related reaction.

Notes: One treatment cycle is 14 days. Target dose is the highest dose administered in Cycle 1. DLT window is 14 days.

a Arm B may open if the planned infusion time exceeds 4 hours on Cycle 1, Day 1.

b If the Day 1 dose is associated with Grade  $\geq 2$  IRR, the ratio may be adjusted so that a smaller percentage of the dose is administered on Day 1, with the remainder of the dose administered on Day 2.

c Arm C may open if more than one patient in Arm B of that dose cohort experiences an IRR that precludes the patient from receiving the full target dose during Cycle 1, Day 1 and Day 2.

Dose escalations will be guided by the modified continual reassessment method of escalation with overdose control (mCRM-EWOC) model (Neuenschwander et al. 2008; [Appendix 11](#)). All cohorts will enroll a minimum of 3 patients. Enrollment of the first 2 patients in each arm of each dose-escalation cohort will be staggered such that the respective Cycle 1, Day 1 treatments are administered  $\geq 72$  hours apart. The maximal

dose escalation increment recommended by the model will be 3-fold. In addition, the relevant demographic, adverse event, laboratory, dose administration, and available PK data will be reviewed prior to dose-escalation decisions, which will be made by an Internal Safety Committee (ISC) in consultation with the investigator (see Section 3.1.5 for more information about the ISC).

Evidence of clinical activity at a given dose level (e.g., decrease in serum monoclonal protein [M-protein]) or PD activity (e.g., NK cell activation) may ungate backfill cohorts at doses that have already completed DLT assessment and have been found not to exceed the MTD in escalation cohorts. DLT information from patients in these back-fill cohorts will be used to inform the mCRM-EWOC model.

Patients will be closely monitored for adverse events during a DLT assessment window (14 days), *as defined above for each arm*. Adverse events identified as DLTs, as defined below (see Section 3.1.1.1), will be reported to the Sponsor within 24 hours.

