Infusion of RO7297089 will be administered as per Table 1, but no higher than 14 mg per kg of body weight per hour ( $\leq 14$  mg/kg/hr). The reason for the restriction in infusion time is due to the use of sucrose as a protein stabilizing agent in the drug product. Sucrose is used as a protein stabilizer in many IV formulations of therapeutics and is generally excreted unchanged in the urine with no detrimental effect to humans. It was commonly used as a stabilizer in various formulations of intravenous Ig (IVIg); however, in 1999, the U.S. FDA issued a “Dear Doctor Letter” noting several cases of renal dysfunction and renal failure with IVIg, and a disproportionate number of cases correlated with sucrose containing formulations of IVIg. The FDA recommended that infusions of IVIg containing sucrose not exceed 3 mg of sucrose/kg/min to avoid renal complications. While this correlation was seen in IVIg formulations, this infusion rate has been extrapolated to any IV product containing sucrose. The amount of sucrose present in the formulated RO7297089 drug product is approximately 61.56 mg of sucrose per milliliter of drug product. Thus, to keep the sucrose infusion rates  $\leq 3$  mg/kg/min, RO7297089 will be infused at a rate no higher than 14 mg/kg/hr. Please refer to the pharmacy manual for additional details on administering RO7297089.

Initially, RO7297089 will be administered over a minimum of 2 hours or longer depending on the patient’s body weight. *The minimum infusion time may be increased if needed to mitigate IRRs.* The infusion may be slowed or interrupted for patients experiencing IRRs (see Section 5.1.2.2). Patients will be observed at least 240 minutes (4 hours) for fever, chills, rigors, hypotension, nausea, or other signs and symptoms of IRRs after the first RO7297089 infusion. *For Arm B (split dose), patients will be observed at least 240 minutes (4 hours) after the Day 1 infusion and for at least 120 minutes (2 hours) after the Day 2 infusion.* At the discretion of the investigator, patients may be hospitalized overnight to accommodate a longer infusion or extend the

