observation period (see Sections 5.3.3 and 5.3.5.11 regarding the reporting requirements for such events). Patients who experience any sign or symptom of an IRR during the first infusion or at any time during the observation period that does not resolve to Grade  $\leq 1$  by the end of the observation period should be observed for at least 24 hours in a hospital setting. In the absence of IRRs, the infusion time of RO7297089 for subsequent infusions *may be reduced as described in Table 1*, to a minimum of 30 minutes. Both of these infusion times will also be dependent on patient's body weight to meet the 14 mg/kg/hr infusion rate limit. *If the first full dose was tolerated, the observation period may also be reduced for subsequent infusions as described in Table 1.*

Patients who undergo inpatient dose escalation (see Section 3.1.3) should receive the first higher dose of RO7297089 over a minimum of 2 hours and be observed for at least 240 minutes (4 hours) for fever, chills, rigors, hypotension, nausea, or other signs and symptoms of IRR.

Management of IRRs and guidelines for dosage and schedule modification and treatment interruption or discontinuation are provided in Section 5.1.2.

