**Table 1 Administration of First and Subsequent Infusions of RO7297089**

RO7297089	Cycle 1, Day 1	Cycle 1, Day 2	Cycle 1, Day 8	Cycle 2, Day 1 and Beyond
Arm A (flat dose)				
Minimum infusion time	120 min	N/A	60 min	30 min
Monitoring window	240 min	N/A	60 min	30 min
Arm B (split dose)				
Minimum infusion time	120 min	120 min	120 min	30 min
Monitoring window	240 min	120 min	120 min	30 min
Arm C (step up dose)				
Minimum infusion time	120 min	N/A	240 min	60 min a
Monitoring window	240 min	N/A	240 min	30 min

N/A = not applicable.

Notes: These infusion and observation times may be longer to meet the 14 mg/kg/hr infusion limit. In addition, these times assume that no infusion-related adverse events occurred during or within 24 hours after the prior infusion. For patients who develop infusion-related adverse events, see Section 5.1.2 for management guidelines.

a After Cycle 2, Day 1, the minimum infusion time may be reduced to 30 minutes provided the previous infusions were tolerated.

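### When the planned Arm B split puts more of the dose on Day 2 than on Day 1, the 120-minute minimum observation after Day 2 could cheaply be raised to 240 minutes

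*Combined protocol and SAP*

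**What the plan says.** Arm B (Synopsis, Dose-Escalation Stage; Section 3.1.1) starts with half the target dose on Day 1 and half on Day 2, then gives the full target dose on Day 8. If the Day 1 part is associated with a Grade 2 or worse IRR, the split may be changed for subsequent patients: "For example, 25% of the target dose administered on Day 1 and the remaining 75% administered on Day 2". Figure 2, footnote b, repeats that "the ratio may be adjusted so that a smaller percentage of the dose is administered on Day 1".

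Section 4.3.2.1 sets Arm B observation at no less than 240 minutes after the Day 1 infusion "and for at least 120 minutes (2 hours) after the Day 2 infusion". Table 1 gives the same two values and no alternative for an unequal split. The table's notes allow longer times to respect the 14 mg/kg/hr limit and add that "these times assume that no infusion-related adverse events occurred during or within 24 hours after the prior infusion".

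On shorter observation, Section 4.3.2.1 says: "If the first full dose was tolerated, the observation period may also be reduced for subsequent infusions as described in Table 1". Section 5.1.1.1 is broader: patients who tolerate infusions well need neither as long an infusion nor as long an observation period later on.

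**The concern.** At 50/50, a shorter watch on Day 2 makes sense, because the patient receives again the amount that was followed by four hours of observation the day before. At 25/75 that reasoning no longer applies. Day 2 is the larger infusion, it comes one day after the patient's first exposure to the drug, and its minimum observation is the shorter of the two. The split would have been changed precisely because earlier patients reacted.

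The issue is patient safety in a first-in-human study. A reaction that begins two to four hours after the Day 2 infusion could occur after the patient has gone home and before the Day 3 visit, which Appendix 1 places 20–24 hours after that infusion. No estimate, sample size or stopping rule depends on it.

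**Working it through.** **1. The plan's own figures.** The text of Section 4.3.2.1 and Table 1 agree for Arm B: 240 minutes after Day 1 and 120 minutes after Day 2. Neither depends on the split.

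**2. Dose ratio, Day 2 share / Day 1 share.**
- 50/50: 0.50 / 0.50 = 1.0
- 25/75: 0.75 / 0.25 = 3.0
- Illustration at 1180 mg, a level on the no-DLT path in Appendix 11, Table 1: 0.25 × 1180 = 295 mg, then 0.75 × 1180 = 885 mg

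**3. Post-infusion minimum.**
- Shortfall: 240 − 120 = 120 minutes
- Hourly post-infusion vital signs (Table 2): 120 / 60 = 2 sets on Day 2, against 240 / 60 = 4 on Day 1

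**4. Other larger later doses in the protocol.**
- Arm C Day 8, the full target dose after 60 mg: 240 minutes (Table 1).
- First higher dose after within-patient escalation: 240 minutes (Section 4.3.2.1), with no minimum step size, in a patient who has completed at least two cycles at the assigned dose (Section 3.1.3). A step from 1180 to 1600 mg, 1600 / 1180 = 1.36-fold, would qualify.
- Arm B Day 2 at 25/75, a 3.0-fold step one day after first exposure: 120 minutes.

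**5. Does the rate limit close the gap?** At the top of the Appendix 11 grid, 1650 mg, Day 2 is 0.75 × 1650 = 1237.5 mg. At an assumed 70 kg, 1237.5 / (14 × 70) = 1.26 hr, or 76 minutes, which is inside the 120-minute infusion floor. The limit lengthens the infusion only below 1237.5 / (14 × 2) = 44 kg.

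**6. Does another safeguard apply?** Take a later patient on a planned 25/75 split who tolerated Day 1 and is well two hours after Day 2.
- The 24-hour hospital rule covers "Patients who experience any sign or symptom of an IRR during the first infusion or at any time during the observation period" that has not settled to Grade 1 or less. This patient has had no reaction.
- The Table 1 note concerns events with the same patient's prior infusion. It refers to Section 5.1.2, where Table 3 sets no observation time.
- Extra vital signs (Section 4.5.5) need a clinical indication or symptoms during the prior infusion.
- Laboratory review before Day 2 (Appendix 1, footnote b) and the report to the sponsor after the first dose (Section 5.1) both come before the period at issue or do not extend it.
- Premedication is mandated before the first administration in Arms A and B. The text does not say whether the Arm B Day 2 infusion counts.
- All the times are minimums and an overnight stay is allowed, but at the investigator's discretion.

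None of these requires this patient to be observed beyond 120 minutes.

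**The case against.** The case for leaving the text alone is substantial.

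- **Tolerated infusions.** Section 5.1.1.1 permits shorter observation after well-tolerated infusions, without asking for a full dose first. On that principle, a patient who tolerated Day 1 may be watched for less time on Day 2. This stands, and it means that the sentence in Section 4.3.2.1 is not decisive by itself.
- **Dose dependence.** Section 3.1.1.1 regards IRRs as generally not dose-related. This weakens an argument based on dose size. It is, however, offered to justify a DLT exception, on general monoclonal-antibody experience. The same protocol adds split and step arms to mitigate IRRs and asks for 240 minutes after larger later doses.
- **Arm B Day 8.** This is the strongest counterexample: 100% of target with 120 minutes. That infusion is 100 / 50 = 2.0 times any earlier one at 50/50, and 100 / 75 = 1.33 times at 25/75. The distinction is that Day 8 follows a completed first full dose and Day 2 does not. That is a judgement about which comparison matters.
- **Comparators.** Arm C Day 8 can be a far larger step (1180 / 60 = 19.7-fold), and within-patient escalation goes above the assigned dose. Arm B Day 2 only completes the assigned dose, one day after a four-hour watch.
- **Opening trigger.** Arm B may open when Arm A's planned Day 1 infusion exceeds 4 hours. The rate limit alone would produce that at 1650 mg only below 1650 / (14 × 4) = 29.5 kg, so the trigger implies an infusion already slowed. If that rate is kept, 75% of the dose takes more than 0.75 × 4 = 3 hours, with vital signs every 30 minutes. Supervised time is then more than 3 + 2 = 5 hours on Day 2, against about 2 + 4 = 6 hours on Day 1 at the infusion floor.
- **Oversight.** The Grade 2 or worse IRR that prompts the change is an adverse event of special interest, reported within 24 hours. The Internal Safety Committee reviews such events.

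A reader might infer that these patients receive half the supervision. The trigger arithmetic does not support that: the halving applies only to the post-infusion minimum.

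**Conclusion.** The point holds as an optional, low-cost safety improvement. For a planned split weighted to Day 2, the post-infusion minimum is 120 minutes shorter than the protocol requires after a first larger dose in two other settings, and no existing rule makes up the difference for a patient who tolerated Day 1 and is well at two hours. The 3.0-fold ratio belongs to the protocol's own 25/75 example; other splits would give other ratios. The subgroup exists only if Arm B opens, a Day 1 reaction occurs and the ratio is then changed.

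Three stronger readings are tempting and are not supported.

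- **That the 120 minutes is a mistake or a contradiction.** The text and Table 1 both state it expressly, and Section 5.1.1.1 offers a rationale.
- **That reactions will be missed at some rate.** Section 5.1.1.1 reports Grade 2 IRRs in 1 of 3 patients at 60 mg and 2 of 2 at 180 mg, before corticosteroid premedication was mandated. It places them during the infusion or within the observation window. No onset times are given, so the frequency of reactions two to four hours after Day 2 cannot be estimated.
- **That Day 2 is infused too fast.** At the 120-minute floor it runs at 75% / 2 hr = 37.5% of target per hour, below the 50% per hour that the floors allow on Arm A Day 1 and Arm B Day 8.

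**What to change.** Add a footnote to Table 1 and a matching sentence in Section 4.3.2.1: for Arm B, when the planned Day 2 share of the target dose exceeds the planned Day 1 share, patients are observed for at least 240 minutes after the Day 2 infusion.

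The trigger should be the planned ratio. A patient on a 50/50 plan may go on to Day 2 after a scheduling shortfall if he or she "has received at least 75% of the intended Day 1 dose". At the limit that gives 0.75 × 50 = 37.5% on Day 1 and 62.5% on Day 2, and it would not set off the longer watch.

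Nothing else needs to change. The 120-minute infusion floor can stay, since Section 4.3.2.1 already allows it to be lengthened to mitigate IRRs. Table 2's Arm B entry for Days 1 and 2 already follows the observation period. The sample two hours after the Day 2 infusion in Appendix 3 is unaffected. The cost is one footnote and one sentence in an amendment, and about 2 more hours on Day 2 for patients on the adjusted split only.
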